1 PROTOCOL SUMMARY

1.1 SYNOPSIS

Title:	Leveraging Ongoing Home Visitation Programs to Address Obesity Disparities Among Underserved, Low-Income Mothers and Children (Obesity Health Disparities Research Center)
Study Description:	This two-arm, parallel, randomized controlled trial (RCT) tests the effectiveness of a simple obesity intervention (HABITS) delivered as part of ongoing home visiting services, compared to the existing home visiting services without obesity-related content on mothers' and children's obesity risks.
Objectives:	The objectives of the study are to compare the effects of treatment on children and primary caregivers' weight outcomes at 6 and 12 months, and to compare the effects of treatment on maternal feeding practices, habit strength of targeted behaviors, and features of the household environment relevant to targeted behaviors at 6 and 12 months.
Endpoints:	The primary endpoint is caregiver and child weight at 12-months
Study Population:	Participants will be 148 mothers (>50% African American; 100% low income) and their children (0–5yo at baseline) enrolled in a home visiting program in central Alabama.
Phase:	N/A
Description of Study Intervention:	The HABITS intervention focuses on habit formation and modifications of food and activity cues in the home to support habit formation. Habit formation is focused on improving five behaviors: 1) fruits/vegetables, 2) fried foods, 3) sugar-sweetened beverages, 4) physical activity and 5) self-monitoring.
Study Duration:	12-months
Subject Duration:	12-months

1.2 SCHEDULE OF ACTIVITIES (SOA)

	Baseline/Enrollment	6-months	12-months
Demographics	X		
Medical history changes		X	X
Caregiver anthropometrics (weight, height)	X	X	X
Child weight	X	X	X
Home food and activity environment (Home Food Assessment; HFA and Home Inventory Describing Eating and Activity Development; H-IDEA)	X	X	X
Habit strength (Self-Reported Habit Index; SRHI)	X	X	X
Food and Activity Frequency Survey (Modified from NHANES)	X	X	X
Personal Health Questionnaire Depression Scale (PHQ-8)	X	X	X

2 INTRODUCTION

2.1 STUDY RATIONALE

Low-income and racial/ethnic minority adults and their young children are especially at-risk of obesity,¹ and the lack of access to evidence-based obesity efforts further contributes to these disparities.^{2,3} Even the most successful obesity prevention strategies have had limited success among under-resourced families, partly because effective obesity interventions are neither accessible nor tailored to address families' poverty, limited education, lack of access to healthier foods and other barriers affecting the ability of these families to adhere to lifestyle changes in real-world settings.^{2,3} While conventional weight management interventions are typically comprehensive, addressing a breadth of nutrition, activity, and behavioral topics,³¹⁻³³ there are a few key behaviors (e.g., self-monitoring of weight, consistent physical activity) that have been consistently associated with long-term weight management.⁴⁻⁸ As such, focusing on helping families develop healthy habits around a few key behaviors may be an effective, more efficient approach to weight management. Further, this type of simplified, targeted approach may be particularly well-suited for under-resourced, overburdened families.⁹ This type of simpler, more targeted intervention focusing on the mastery of a few, simple behaviors is consistent with a habit-formation paradigm, which focuses on frequently and consistently engaging in a target behavior in response to a specific cue until that behavior becomes automatic.^{9,34-38} Given that habit-formation and automaticity rely on repeated engagement in the target behavior in response to consistent contextual cues, it is necessary that such an intervention include modification of cues in the household environment, where most food is consumed among US families, in order to support the development and maintenance of targeted healthy behaviors. Thus, the proposed study is focused on implementing an obesity-prevention intervention that prioritizes the habit-formation of a few behaviors from multi-component, evidence-based obesity interventions while addressing relevant cues in the home environment to support habit-formation of targeted behaviors. The current intervention is embedded within an ongoing federally funded home visiting program, which provides an ideal infrastructure for engaging historically underserved caregivers and their children within their homes. By embedding the study intervention into an existing home visiting program, dissemination and scalability of the study intervention (if effective) is feasible.

2.2 BACKGROUND

Obesity and health-related disparities persist among socioeconomically disadvantaged adults and children. Although a nationally representative study found a decline in obesity for children ages 0-5, this was not true for economically disadvantaged children.¹⁰ In fact, 40% of low-income children enrolled in federally-funded programs are overweight ($\geq 85^{\text{th}}$ BMI percentile) by age five, with an obesity ($> 95^{\text{th}}$ percentile) prevalence of 16.3% among low-income 2-4yo children in Alabama.¹¹⁻¹⁴ Similarly, low-income women and those with less education are disproportionately affected by obesity.¹ Even the most successful obesity reduction/prevention strategies have had limited impact among under-resourced families, partly because effective obesity interventions are neither accessible nor tailored to address families' poverty, limited education, lack of access to healthier foods and other barriers affecting the ability of these families to adhere to lifestyle changes in real-world settings.^{2,3}

Maternal behaviors and the home environment are likely key pathways of obesity risk in early childhood.^{15,16} Maternal factors such as mothers' diet and feeding practices are instrumental in shaping children's health behaviors and weight outcomes.¹⁷⁻²¹ Similarly, a variety of factors within the home environment have also been associated with healthful dietary behaviors. For instance, both household

food availability (foods present in the house) and accessibility (whether available foods are in a form or location that facilitates their consumption, such as fruit on the counter) are associated with children's dietary intake and weight status.²²⁻²⁴ Since health behaviors developed in early childhood influence habits and weight trajectories across the lifecourse,^{17,18,25-30} interventions are needed to address these pathways early in the child's development. These findings support our effort to explicitly tackle maternal factors as well as the home environment as key determinants of children's weight trajectories.

Simple, targeted interventions focused on habit-formation may be efficient and effective. While conventional family-based obesity interventions comprehensively address nutritional, physical activity, and behavioral topics,³¹⁻³³ only a handful of behaviors (e.g., self-monitoring of weight, consistent physical activity, regular eating patterns) have been consistently, and empirically, associated with long-term weight management.⁴⁻⁸ Thus, helping individuals develop healthy habits around a few key behaviors may be as effective and more efficient for impacting energy balance and weight management than addressing a wide-ranging set of topics. A simplified approach targeting a select number of behaviors may be particularly well-suited for under-resourced settings and populations.⁹ This approach is also consistent with the growing literature supporting habit-formation for weight management.^{9,34-38} Habit-formation interventions focus on frequently and consistently enacting a target behavior within a certain context or in response to a specific cue until the behavior reaches automaticity.^{9,34-38} Once habits are well-established (i.e., automatic), then they become less reliant on intentional control or awareness and more resistant to competing demands (e.g., mental fatigue, negative affect).³⁸ A handful of studies suggest that habit-formation interventions focused on select energy-balance behaviors (e.g., reducing fat, increasing daily steps, consuming low-energy dense snacks, controlling portions, decreasing intake of sugar-sweetened beverages, reducing sitting time) are feasible and result in greater weight loss than usual care when delivered in primary care^{9,34,39} and are effective in improving parental feeding practices (i.e., increased provision of fruit/vegetables and healthy snacks, decreased serving of sweetened drinks) for children ages 2-6yo.⁴⁰

Helping families modify their home environment may facilitate habit-formation. Since habit-formation and automaticity rely on the repetition of a behavior in response to consistent contextual cues, it is imperative to address the cues in the individuals' personal and household environment that are conducive to the development and maintenance of targeted healthy habits. Modification of household cues to support behavior change- such as increasing the availability of washed and cut fruits/vegetables and the visibility of cues to promote physical activity, or removing energy-dense foods from the home or storing in inaccessible locations- is grounded in the principles of "choice architecture", which posits that our environment ultimately determines the choices we make (i.e., breakfast choice is determined by breakfast options available).⁴¹⁻⁴⁴ Two recent trials examined the effectiveness of modifications in the participants' household environment on weight management.^{45,46} Treatment resulted in significant weight loss in these predominantly White, well-educated samples,^{45,46} and outcomes seemed particularly promising for women and other adults living in the household.⁴⁷ However, less is known about the utility of these household environmental modifications for addressing obesity in underserved and low-income women and their children.

The proposed study leverages an established home visiting program to deliver an in-home obesity intervention to underserved mothers and children who would otherwise not receive these services. Consistent with a capacity building approach, we aim to extend the curriculum and mission of an ongoing home visiting program to address obesity and related health disparities among low-income women and children (see also⁴⁸). Home visiting programs are embedded in a comprehensive system of child and maternal health designed to optimize child development and prevent adverse outcomes.⁴⁹⁻⁵³

These programs are effective in improving children's physical and psychosocial health, immunization rates, breastfeeding, and overall cognitive and social development.^{47,53-70} The home visiting infrastructure is ideal to address obesity among underserved mothers and children because it: (1) already engages low-income families at a critical point in the intergenerational transmission of obesity; (2) provides in-home services to address ecologically relevant cues and promote generalization to the family environment;^{71,72} (3) removes many of the barriers of outpatient programs (e.g., transportation, childcare need); (4) provides services for an extended period of time to ensure mastery of skills and behaviors; and (5) is already implemented in urban and rural areas nationwide,^{58,68,73,74} which would facilitate future dissemination and scalability. To date, however, there has been no comprehensive effort to address maternal-child obesity as part of these home visiting services.

2.3 RISK/BENEFIT ASSESSMENT

2.3.1 KNOWN POTENTIAL RISKS

This study involves providing a health behavior intervention to low-income mothers or primary caregivers and children; therefore, the use of children as participants is inherent to the nature of this protocol. If a mother becomes pregnant during the course of the study, we decided not to exclude or discontinue her from the study, as the habit behaviors pose no risk and are likely beneficial to her as well as her unborn child but are also primarily aimed at providing healthy options for the child in the study. The study intervention, which is aimed to improve health behaviors of mothers or primary caregivers and children, is considered low-risk. Additionally, because the study assessments only involve completion of interviews, surveys, vitals, and home food assessments, there is still less than minimal risk to participants. There is a low risk of emotional or psychological discomfort from participants answering personal questions about their eating and activity behaviors. There is also a possible minimal, mild, and temporary risk for physical overexertion due to exercise from increased walking and physical activity. To protect the rights and welfare of these participants, they will be assured that their regular home *visiting* services will in no way be affected by their decision to participate, or not participate, in the study. While we are offering financial incentives to mothers or primary caregivers, these incentives are modest and are only intended to compensate for time completing assessments.

In our preliminary work providing these services, mothers or primary caregivers did not report increased burden from participating in this program. Participants receiving the obesity prevention curriculum were just as likely to meet the benchmark areas defined by Health Resources and Services Administration for evaluating the conventional home visiting program, which suggests that the additional obesity prevention content did not detract from the existing services or over-burden participants receiving the combined program. Also, participants were 27% less likely to discontinue home visiting services when they received the combined home visiting + obesity prevention curriculum as compared to those receiving the conventional program alone in our prior preliminary work.

2.3.2 KNOWN POTENTIAL BENEFITS

By targeting children and their mothers or primary caregivers, the current intervention has the potential to improve maternal behaviors and outcomes while also addressing the intergenerational transmission of obesity by testing whether maternal factors and home environment mediate children's outcomes. The intervention has the potential to reduce obesity and risk factors associated with obesity for participating mothers or primary caregivers and their children and targets a specific population that carries a disproportionate burden of obesity. This initiative represents a unique opportunity to increase access to

obesity treatment/prevention services by leveraging an ongoing home visiting infrastructure that provides family-oriented services to families most at risk for health and obesity disparities. This partnership greatly improves the potential to disseminate cost-effective and sustainable evidence-based obesity efforts on a larger scale. This 12-month intervention will provide important information about the effectiveness of this intervention delivered within the home environment of low-income families. Finally, if the program intervention is deemed successful, the program can easily be implemented in conjunction with hundreds of other similar home visiting services to reduce the impact and prevalence of obesity on low-income families and children throughout Alabama and other states.

3 STUDY DESIGN

3.1 OVERALL DESIGN

This is a cluster randomized trial in which home visitors (n=18 anticipated) employed by our partner (First Teach Home Visiting Program) will be randomly assigned to deliver the home visiting standard curriculum with or without HABITS (n=9 home visitors in each arm).

Caregivers with a child 0-5 years of age who are enrolled in the First Teacher Home Visiting program and who have completed their initial 90-day home visiting program benchmark testing will constitute our initial recruitment pool (>50% African American, 40% White, <10% other/multiple race). First Teacher Home Visiting Program enrolls caregivers with young children in their free and voluntary services through community outreach. In order to be eligible for home visiting services, families must have a social risk factor such as poverty, social isolation, lack of material and social support, lack of transportation and limited education and literacy.

Home visitors will approach their families who are potentially eligible to introduce the study, gauge interest, and screen interested families for eligibility. Designated study staff determine of families are eligible based on the completed screening form and inclusion/exclusion criteria. Home visitors are informed of family's eligibility and notify the family. Eligible families are then introduced to a blinded study assessment worker who schedules the enrollment and baseline visit.

Assessment workers (who are distinct from home visitors and masked to group assignment) will be responsible for completing informed consent, enrolling caregiver-child dyads into the study, and completing Visit 1 (baseline), Visit 2 (6-month), and Visit 3 (12-month) assessments.

After completing Visit 1 (baseline) assessment procedures, families will be told by their home visitor which study arm they have been allocated to, for those in the HABITS intervention arm (i.e., home visiting standard curriculum with HABITS) will begin receiving the HABITS intervention at their home visits for 12-months.

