3.2 END OF STUDY DEFINITION

While Primary Completion will be defined as the date of the last 12-month assessment data collection of the last participant, the End of Study will be the date that caregiver-child benchmark data and home visit completion data have been received from our home visiting program partner, as these data will provide necessary covariates for the conduct of our statistical analyses and are needed to ensure the study does not affect family services

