4 STUDY POPULATION

4.1 INCLUSION CRITERIA

Families enrolled in home visiting will be invited to participate in the study, with limited exclusion criteria. Caregiver-child dyads will be eligible to participate regardless of weight status because the targeted health behaviors are relevant and beneficial for all caregivers and children. Improvements in maternal behaviors (regardless of weight status) may further reduce children's obesity risk. To be included, caregiver-child dyads will have to meet the following inclusion criteria:

- Caregiver enrolling in the trial is 18 years of age or older
- Child is 0-5 years of age
- Child has at least 1 year of eligibility remaining in the home visiting program
- Family has completed their first 90-days in the home visiting program

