4.4 STRATEGIES FOR RECRUITMENT AND RETENTION

Individuals who are enrolled in the First Teacher Home Visiting program and who have completed their initial 90-day home visiting program benchmark testing will constitute our initial recruitment pool. Home visitors will approach their families who are potentially eligible to introduce the study, gauge interest, and screen interested families for eligibility. Designated study staff determine of families are eligible based on the completed screening form and inclusion/exclusion criteria. Home visitors are informed of family's eligibility and notify the family. Eligible families are then introduced to a blinded study assessment worker who schedules the enrollment and baseline visit.

The unique relationship between home visitors and mothers facilitates retention. Many of these caregivers are socially isolated and home visitors are important sources of support. We will also use strategies (implemented with participants in both intervention arms) that we have found effective for retention: (1) providing gift cards of \$100 at each data collection for all caregivers, with all incentives paid after each assessment; (2) ensuring frequent contacts with all participants to maintain engagement and foster open communication; (3) sending holiday newsletters to update participants about study activities; (4) acknowledging birthdays and milestones; (5) providing reminder phone calls before assessment sessions; and (6) seeking contact information of relatives or friends to be able to reach participants.

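### The randomised home visitors approach and screen their own families; the plan does not say when they learn their arm and describes no record of families not approached

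*Combined protocol and SAP*

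**What the plan says.** Sections 3.1 and 5.2 randomise 18 home visitors, nine to each arm. Section 3.1 gives the same visitors the first steps of recruitment: "Home visitors will approach their families who are potentially eligible to introduce the study, gauge interest, and screen interested families for eligibility". Section 4.4 repeats this: "Home visitors will approach their families who are potentially eligible to introduce the study".

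Later steps are taken by others. On eligibility, section 3.1 says: "Designated study staff determine of families are eligible based on the completed screening form and inclusion/exclusion criteria". Consent, enrolment and all assessments fall to a separate group: "Assessment workers (who are distinct from home visitors and masked to group assignment"). After Visit 1, "families will be told by their home visitor which study arm they have been allocated to".

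On coverage, section 4.1 says: "Families enrolled in home visiting will be invited to participate in the study, with limited exclusion criteria". The same section makes dyads eligible whatever their weight status. Section 4.4 says that families past the 90-day benchmark "will constitute our initial recruitment pool".

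Section 5.2 argues that bias from cluster randomisation is reduced because all mothers have low income and the race mix is fairly even. It adds that training and supervision are separate by arm, without dating either relative to recruitment.

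On adjustment, sections 8.3 to 8.3.2 refer to demographics and other measured covariates. Section 3.2 says of the programme benchmark and home visit completion data that "these data will provide necessary covariates for the conduct of our statistical analyses".

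**The concern.** In a cluster trial, randomising the visitors balances the visitors and their caseloads in expectation. It does not balance the families who enrol if the person deciding whom to approach knows the arm. All families of one visitor share an arm, so a visitor who has told one family its allocation knows the allocation of every family approached afterwards.

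The arms also ask different things of visitors. HABITS adds weekly check-ins between visits (5.1.2) and a weekly checklist (5.3). That could change how many families are put forward without changing the mix, or it could shift the mix in either direction.

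If the mix differs in expected weight change, part of a 12-month difference between arms would reflect recruitment. A larger sample does not remove this. The baseline comparison in 8.3.5 covers enrolled families only, so it cannot show who was never approached.

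**Working it through.** **Tracing the recruitment path**

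1. Who is approached: the home visitor decides in practice (3.1, 4.4). Section 4.1 says that enrolled families will be invited, but no described step verifies it.
2. Who is screened: the visitor screens families who express interest. A screening form is described for these families only.
3. Who is eligible: study staff decide, from that form.
4. Who consents: masked assessment workers obtain consent.
5. When families learn the arm: after Visit 1, from the visitor.

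Steps 3 to 5 act only on families already put forward. The documents describe no log of families not approached or not interested. Section 4.3 says only how ineligible dyads are informed, and the 5.3 checklist covers contacts with participants in the HABITS arm.

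**When could visitors know their arm while recruiting?**

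No section states the timing. Some text is compatible with staggered entry: the initial pool (3.1, 4.4), replacement of some randomised subjects (6.2), and primary completion tied to the last participant (3.2). The synopsis points the other way, since it gives both study and subject duration as 12 months. The documents leave the question open.

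**The plan's own sample size, as background**

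For 0.53 SD, two-sided 5% and 80% power, the exact t-test needs 57 per group. With 59 per group, power is about 81%, close to the stated 80%. The stated total of 140 is reproduced if 59 per group already includes the clustering inflation: 112 × 1.052 = 117.8, and 117.8 / 0.85 = 138.6, which rounds up to 70 per group. No sample size figure changes because of this point.

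**Illustration of size (the shifts are assumptions, not in the documents)**

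Suppose 10% to 20% of one arm is shifted by 0.3 to 0.5 SD in expected weight change, with no treatment effect.

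- Bias = 0.10 × 0.3 = 0.03 SD, up to 0.20 × 0.5 = 0.10 SD. Divided by 0.53, this is 6% to 19% of the target effect.
- N=140 with 15% attrition: 140 × 0.85 / 2 = 59.5 per arm, and 119 / 18 = 6.61 per visitor.
- Inflation with ICC 0.01: 1 + 5.61 × 0.01 = 1.056. Effective n = 59.5 / 1.056 = 56.3 per arm. SE = √(2 / 56.3) = 0.188 SD.
- Type I error comes from the noncentral t distribution with 18 − 2 = 16 df, two-sided 5%, noncentrality = bias / SE.

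| Assumed bias (SD) | Noncentrality, N=140 | Type I error, N=140 | Type I error, N=148 |
|---|---|---|---|
| 0.03 (10% × 0.3) | 0.159 | 5.3% | 5.3% |
| 0.05 (10% × 0.5) | 0.265 | 5.7% | 5.8% |
| 0.06 (20% × 0.3) | 0.318 | 6.0% | 6.1% |
| 0.10 (20% × 0.5) | 0.531 | 7.9% | 8.1% |

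The N=148 column uses the synopsis total (62.9 per arm after attrition, inflation 1.060, effective n 59.3, SE 0.184). If adjustment removed half of the bias in the 20% cases, 0.03 to 0.05 SD would remain, or 5.3% to 5.7% at N=140.

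**Room to select**

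Families enrolled per visitor: 140 / 18 = 7.8, or 148 / 18 = 8.2. Caseload size is not given. If caseloads are close to 8, nearly every family must be enrolled and there is little room to select.

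**The case against.** The strongest reply is that this is an unstated detail and not a demonstrated flaw. No section says that visitors know their arm while recruiting, and one sentence on timing could settle the matter. The signs of staggered entry are weak. An initial pool can mean the starting pool before screening, and the 6.2 replacement rule speaks of individual subjects being randomised, which fits poorly with visitor-level allocation. This stands, and it is why the point is conditional.

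The plan also has real safeguards: staff eligibility decisions, masked consent, disclosure after baseline, eligibility regardless of weight, equal incentives in both arms, and a primary analysis of weight change, so that a difference in baseline weight alone is not an arm effect. These reduce the concern. None of them governs who is approached.

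Baseline adjustment may remove part of any difference, since demographics, SRBAI, PHQ-8 and BRIEF-A are collected at Visit 1. No covariate list is fixed, however.

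A reader might infer that nothing anywhere records the families passed over. The documents do not support that. Section 9.1.4 refers to written SOPs that are not shown, and the programme presumably knows its own caseloads. The supportable statement is that no such record is described.

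**Conclusion.** The point holds as a gap in the recruitment procedure that is cheap to close. The randomised visitors recruit from their own caseloads, their masking and the timing of their knowledge are not described, and the 5.2 argument on income and race mix does not address who is approached.

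A reader might go further and conclude that visitors recruit knowing their arm, or that the trial result will be biased. The documents support neither: knowledge of arm during recruitment is an inference that depends on families entering over time.

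Size and direction are unknown. The figures of about 5.3% to 8.1% type I error rest wholly on assumed shifts placed in one arm, and should not be cited as an estimate for this trial. Under those assumptions the effect is modest, and small caseloads would reduce it further. Without an approach log, though, the sponsor would find it hard to show later that recruitment was even.

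A related point on adjustment does not depend on timing. Home visit completion arises after allocation and can be affected by the arm, so it cannot correct for recruitment differences and may distort the treatment effect if used as a covariate.

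**What to change.** **Sections 3.1 and 4.4.** The programme, not the visitor, draws from its own records a list of the families on each caseload who meet the criteria it holds (caregiver age, child age, remaining programme eligibility, 90-day milestone). This is done before visitors learn their allocation where that is still possible, and otherwise now. Newly eligible families are added by the same criteria. Every listed family is offered the study with one script. Any replacement under 6.2 comes from the same list.

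**Logging.** Record listed, approached, eligible and consented counts by visitor, and report them by arm.

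**Section 5.2.** State when visitors learn their allocation relative to approaching families, and add the list procedure to the existing text on bias.

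**Sections 3.2 and 8.3.** Limit adjustment covariates in the primary models to those measured before allocation or at baseline. Report home visit completion descriptively.

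**Cost.** No change to sample size, outcomes or intervention. The costs are list administration, and partner and IRB agreement on sharing coded entries, noting that 9.1.1.1 requires written consent before screening procedures. Some visitor influence on uptake remains, because the visitor still makes the offer.
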